20 USE OF INFORMATION AND PUBLICATION

BioMarin recognizes the importance of communicating medical study data and therefore encourages the publication of these data in reputable scientific journals and at seminars or conferences. The details of the processes of producing and reviewing reports, manuscripts, and presentations based on the data from this study will be described in the Clinical Trial Agreement between BioMarin and the Investigator/Institution. Consideration for authorship of all publications will be based on compliance with the Uniform Requirements for Manuscripts Submitted to Biomedical Journals (“Uniform Requirements”) of the International Committee of Medical Journal Editors (ICMJE) (<http://www.icmje.org/about-icmje/faqs/icmje-recommendations/>) and good publication practices (GPP).

22 INVESTIGATOR RESPONSIBILITIES

22.1 Conduct of Study and Protection of Human Subjects

In accordance with FDA Form 1572 and/or principles of ICH E6 GCP, the Investigator will ensure that:

- He or she will conduct the study in accordance with the relevant, current protocol and will only make changes in a protocol after notifying the sponsor, except when necessary to protect the safety, rights, or welfare of subjects.
- He or she will personally conduct or supervise the study.
- He or she will inform any potential subjects, or any persons used as controls, that the drugs are being used for investigational purposes. He or she will ensure that the requirements relating to obtaining informed consent in 21 CFR Part 50 and/or ICH E6 Sections 2.9 and 4.8 are met, as well as IRB/IEC review and approval requirements in 21 CFR Part 56 and/or ICH E6 GCP Section 2.6.
- He or she will report to the sponsor adverse experiences that occur in the course of the investigation in accordance with 21 CFR 312.64 and/or ICH E6 GCP Section 4.11.
- He or she has read and understands the information in the Investigator's Brochure, including potential risks and side effects of the drug.
- His or her staff and all persons who assist in the conduct of the study are informed about their obligations in meeting the above commitments
- He or she will ensure that adequate and accurate records are in accordance with 21 CFR 312.62 and/or ICH E6 Section 4.9, and will make those records available for inspection in accordance with 21 CFR 312.68 and/or ICH Section 4.9.7.
- He or she will ensure that the IRB/IEC/REB complies with the requirements of 21 CFR Part 56, ICH Section 3.0 and other applicable regulations, and conducts initial and ongoing reviews and approvals of the study. He or she will also ensure that any change in research activity and all problems involving risks to human subjects or others are reported to the IRB/IEC/REB. Additionally, he or she will not make any changes in the research without IRB/IEC/REB approval, except where necessary to eliminate apparent immediate hazards to human subjects.
- He or she agrees to comply with all other requirements regarding the obligations of clinical Investigators and all other pertinent requirements in 21 CFR Part 312 and/or ICH E6 R2.

1 RATIONALE AND SUMMARY OF CHANGES

The protocol has been amended to include the following changes:

1. The lower age range of participating subjects who have a \geq 6-month period of pretreatment growth assessment in Study 111-901 immediately before study entry has been revised from \geq 3 months to \geq 6 months [§9.1].

Rationale: To harmonize the roll-over of subjects from Study 111-901 to 111-206 in each cohort.

2. No two sentinel subjects will be dosed on the same day for any cohort [§9.1].

Rationale: To enforce a minimum period of safety observation prior to dosing the next subject, as in each cohort, the sentinel subjects will be the youngest children to date dosed with BMN 111.

3. Echocardiogram will be performed at the Week 56 Safety Follow-up and Early Termination visits [Table 9.1.1; §12.1.10; §12.1.11].

Rationale: To enable monitoring for any unintended adverse anatomical or functional cardiac adverse effects at the time of study completion.

4. Use of residual plasma samples for cGMP PD biomarker assessment in all age groups has been added to procedures [Table 9.1.1; Table 9.11.6.4.1; §12.1.2; §12.1.7; §12.1.8; §12.1.9].

Rationale: Use of the residual sample allows for PD assessments in infants without timed urine collection. The infant group assessments can then be compared to all age groups.

5. An anti-BMN 111 immunogenicity assessment has been added at Week 3 [Table 9.1.1; §12.1.5].

Rationale: Week 3 immunogenicity assessment has been added to characterize early anti-BMN 111 immune responses in this age range of the achondroplasia subject population.

6. Bone metabolism urine biomarkers, BMN 111 pharmacodynamic urine biomarkers, and urine chemistry assessments have been added at Week 39 [Table 9.1.1; §12.1.8].

Rationale: To obtain PD assessments at each visit that PK is collected and to obtain creatinine concentrations for cGMP calculations

7. The sleep study scheduled at the Week 26 visit has been removed [Table 9.1.1; §12.1.7].

Rationale: To minimize study burden on the trial participants, families and caregivers, as only two polysomnography studies are required to meet the study objectives. One

assessment will be performed at baseline and one at Week 52 (or the Early Termination Visit, if the subject leaves the study early).

8. DXA scans will no longer include tibia scans [Table 9.1.1; §9.11.4.2].

Rationale: The tibia scan was removed because DXA machines are unable to properly perform the scan.

9. If the 111-901 visit at which the subject enters Study 111-206 and the 111-206 Screening visit are on the same day, the procedures common to both visits will be performed one time only [Table 9.1.1 (footnote b)].

Rationale: To ensure that duplicate study procedures, including blood draws, are not repeated unnecessarily in this infant and toddler population.

10. On days when PK samples are being drawn, ECG will be performed within a 5-minute window prior to the 30-minute PK assessment [Table 9.1.1 (footnote h); §9.11.6.7].

Rationale: This timing allows for ECG assessment in relation to BMN 111 C_{max}.

11. Exclusion criterion #6 has been revised from “...as determined by the Investigator *based on* the following assessments...) to (...as determined by the Investigator *and informed by* the following assessments...). The determination about whether presence of cervicomedullary compression is likely to require surgical intervention will be informed by physical exam, polysomnography, and MRI [§9.3.2].

Rationale: To clarify that this is a clinical decision to be informed by signs, symptoms, and investigations, and not based solely on abnormal finding in an MRI.

12. Exclusion criterion #15 has been revised to include cervicomedullary decompression surgery (Cohorts 2 and 3 only) [§9.3.2].

Rationale: To clarify that children with prior cervicomedullary decompression surgery are not eligible for entry into the study in Cohort 2 or 3. This is to enable formal evaluation of a potential treatment effect on the foramen magnum using MRI in children at ages where the foramen magnum is still growing rapidly. As the synchondroses around the foramen magnum are already closing after the age of two years, subjects with prior cervicomedullary decompression surgery may be allowed into Cohort 1 only after discussion and agreement with the Medical Monitor.

13. Inclusion/exclusion criteria have been added for Cohort 3 subjects enrolling in the observational period [§9.3.3; §9.3.4].

Rationale: These criteria are used in our observational study 111-901 and apply only to Cohort 3 subjects who enroll in the 111-206 observation period.

14. A table of restricted medications, including growth hormone, has been added [§9.3.5].

Rationale: To ensure that growth hormone is not used concomitantly.

15. In Section 9.11.4.4, Genomic Biomarker Analysis, the text “of plasma DNA” has been removed from “Exploratory genomic analysis of plasma DNA may inform understanding of the BMN 111 mechanism of action...” [§9.11.4.4].

Rationale: Genomic analysis implies DNA/RNA analysis, and we are not obtaining DNA from plasma.

16. For subjects enrolled in Cohort 3 (0 to < 6 months old), the collection period for all AEs begins after informed consent is obtained [Table 9.1.2 footnote h; §10.2.1].

Rationale: to collect and document all AEs so as to establish robust baseline natural history in these subjects prior to study drug administration.

17. Administrative updates have been made to improve consistency and clarity.

- a. Text has been changed to reflect the age of majority rather than age 18, as the age of majority varies between countries. Section 5.3, *Subject Information and Informed Consent*.
- b. Section 7.3, *Ongoing Clinical Studies*, has been updated to include a description of Study 111-302 (Section 7.3.5).
- c. In Section 8, *Study Objectives*, in the secondary objective addressing evaluation for hip, thigh, or knee pain, or change in gait *from medical history*, the phrase “...from medical history...” has been removed to clarify that hip assessments are performed at screening, and these measures serve as a baseline for future assessments.
- d. Error in Section 9.1, *Overall Study Design and Plan*, description of Cohort 3 has been corrected to state that at least 17 additional subjects will be randomized.
- e. Clarification about age-appropriate dose adjustment has been added to indicate that subjects will be administered the recommended dose appropriate to their current age. Section 9.1, *Overall Study Design and Plan*, and Section 9.1.1, *Dose Adjustments*.
- f. The time window for the Week 56 safety follow-up visit has been changed from \pm to + 7 days to allow a full 4 weeks between the last dose of study drug and the safety follow-up visit. Table 9.1.1, Section 12.1.10, *Week 56 Safety Follow-up*.
- g. Clarified that the screening/baseline hip assessment includes a pelvis x-ray. Table 9.1.1, Section 12.1.1, *Screening/Baseline Day -30 to Day -1*.
- h. Because the definition of ACH-related events differed between sites, capture of ACH-related events has been changed to capture all procedures listed in the Schedule of Events to ensure all procedures are collected and analyzed. Tables 9.1.1 and 9.1.2; Section 9.11.6.2; Sections 12.1.2-12.1.11; Sections 12.2.2-12.2.3.

- i. Vital signs instructions now include sitting or supine positions to account for subjects who are too young to sit. The duration of vital signs assessments in Section 9.11.6.5 and Table 9.11.6.5.1 has been extended to align with the assessments presented in the SOE. Additionally, if a dose adjustment visit coincides with a visit at which a full PK is drawn, vital signs will be obtained for 8 hours, similar to the Day 1,2 schedule. Table 9.1.1, *Vital Sign Assessment Frequency* table; Section 9.11.6.5, *Vital Signs*; Table 9.11.6.5.1.
- j. In the event that a sentinel subject has an interrupted dose of study drug on Day 1, instructions have been included for a change in the PK collection schedule. Table 9.1.1 footnote L; Section 9.11.5, *Pharmacokinetics Variables*.
- k. Footnote m in Table 9.1.1 has been updated to correspond to the information in Section 9.11.6.10, *Anti-BMN 111 Immunogenicity Assessments and IgE Testing*.
- l. In Table 9.1.1, footnotes n and o, and Section 9.11.3, *Secondary Efficacy Variables*, text has been added to specify the biomarkers used to assess changes in bone and collagen metabolism.
- m. In Table 9.1.1, footnote q, instruction has been included that efforts to obtain a satisfactory MRI image can be discontinued after 3 unsuccessful attempts.
- n. In Table 9.1.1, footnote v now includes instructions for managing a dose interruption.
- o. Section 9.1.1, *Dose Adjustments*, has been corrected to state that a DMC review will occur after the third sentinel subject reaches Week 12 post-dose adjustment.
- p. In Section 9.3.8, *Duration of Subject Participation*, final follow-up visit for subjects who discontinue from the study has been changed from 2 weeks to 4 weeks after last dose to be consistent with the safety follow-up at 4 weeks in the Schedule of Events.
- q. In Section 9.4.1, *Treatments Administered*, text has been added to reiterate that sentinel subjects will be treated with BMN 111, versus randomized subjects who will receive either BMN 111 or placebo. Additionally, the BMN 111 dose level is subject to potential per-protocol adjustment.
- r. Directions for subject observation following BMN 111 administration at study visits has been revised in Section 9.4.1.1, *Study Drug Administration*, for consistency with Section 9.4.4, *Directions for Administration*.
- s. Text in Section 9.4.1.1, *Study Drug Administration* now indicates that study drug injections will be administered at age-appropriate sites, determined at the discretion of the investigator.
- t. Text has been revised to indicate that in the hour prior to injection, all subjects should be well hydrated and fed. Section 9.4.4, *Directions for Administration*; Section 9.6, *Dietary or Other Protocol Restrictions*.
- u. In Section 9.4.5, *Method of Assigning Subjects to Treatment Groups*, a note has been added that in Japan, subjects are randomized separately within each cohort.

- v. Section 9.11.4.2, *Imaging Assessment Procedures*, has been corrected by removing lateral views from bilateral lower extremity x-rays, and clarified to state that bilateral lower extremity x-rays, anterior-posterior (AP) view, are done to assess growth plate morphology. Instruction has been added to contact the medical monitor to discuss alternate non-radiological methods for assessment if there are IRBs or IECs unwilling to allow x-rays in Cohort 3 subjects (also, Table 9.1.1, footnote t). Additionally, the list of DXA acquisitions has been clarified.
- w. Section 9.11.4.7.1, *Bayley-III*, has been revised to remove reference to the Social-Emotional and Adaptive Behavior Scale components because these scales will not be used in this study. Additionally, the duration of the assessment has been clarified.
- x. In Section 9.11.4.7.4, *Child Behavior Checklist*, the duration of the assessment has been clarified.
- y. In Section 10.1.2, the statement that hospitalization for less than 24 hours will not be considered an SAE has been deleted to make the criterion consistent across all BioMarin protocols. Section 10.1.2, *Serious Adverse Events*.
- z. Error in Table 10.2.3.3.1 has been corrected to read “The AE could *not* be explained by factors or causes other than exposure to the IP”

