10.1.1 Adverse Events

For this protocol, a reportable adverse event (AE) is any untoward medical occurrence (e.g., sign, symptom, illness, disease or injury) in a subject administered the study drug or other protocol-imposed intervention, regardless of attribution. This includes the following:

- AEs not previously observed in the subject that emerge during the course of the study.
- Pre-existing medical conditions judged by the Investigator to have worsened in severity or frequency or changed in character during the study.
- Complications that occur as a result of non-drug protocol-imposed interventions (eg, AEs related to screening procedures, medication washout, or no-treatment run-in).

An adverse drug reaction is any AE for which there is a reasonable possibility that the study-drug caused the AE. “Reasonable possibility” means there is evidence to suggest a causal relationship between the study-drug and the AE.

Whenever possible, it is preferable to record a diagnosis as the AE term rather than a series of terms relating to a diagnosis.

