10.2.3.3 Causality

The Investigator will determine the relationship of an AE to the study drug and will record it on the source documents and AE eCRF. To ensure consistency of causality assessments, Investigators should apply the guidance in [Table 10.2.3.3.1](#).

Table 10.2.3.3.1: Causality Attribution Guidance

Relationship ^a	Description
Not Related	
 • Exposure to the IP has not occurred 
OR • The administration of the IP and the occurrence of the AE are not reasonably related in time 
OR • The AE is considered likely to be related to an etiology other than the use of the IP; that is, there are no facts, evidence, or arguments to suggest a causal relationship to the IP.
Related	
 • The administration of the IP and the occurrence of the AE are reasonably related in time 
AND • The AE could possibly be explained by factors or causes other than exposure to the IP 
OR • The administration of IP and the occurrence of the AE are reasonably related in time 
AND • The AE is more likely explained by exposure to the IP than by other factors or causes.

Factors suggestive of a causal relationship could include (but are not limited to):

- Plausible temporal relationship
- Absence of alternative explanations
- Rarity of event in a given subject or disease state
- Absence of event prior to study drug exposure
- Consistency with study product pharmacology
- Known relationship to underlying mechanism of study drug action
- Similarity to adverse reactions seen with related drug products
- Abatement of AE with discontinuation of study drug, and/or recurrence of AE with reintroduction of study drug

The investigator's assessment of causality for individual AE reports is part of the study documentation process. Regardless of the Investigator's assessment of causality for individual AE reports, the Sponsor will promptly evaluate all reported SAEs against cumulative product experience to identify and expeditiously communicate possible new safety findings to investigators and applicable regulatory authorities.

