9.1.2 Stopping Criteria

Individual Subject Stopping Criteria

For individual subjects treated with BMN 111, DMC will be informed if any of the following individual subject stopping criteria should occur. Temporary dosing suspension, permanent discontinuation of dosing, or dose reduction for the individual subject will be considered.

- Any treatment-emergent adverse event (AE) assessed as at least Grade 4 by the Investigator and/or Sponsor Medical Monitor
- Any treatment-emergent AE of at least Grade 3 assessed as related to study drug by the Investigator and/or Sponsor Medical Monitor
- Any two treatment-emergent Grade 2 symptomatic hypotension events within 7 days (non-urgent medical intervention indicated) or any Grade 3 hypotensive event (urgent medical intervention or hospitalization indicated) assessed by the Investigator and/or Sponsor's Medical Monitor
- Clinically significant finding or arrhythmia on ECG that indicates abnormal cardiac function or conduction or prolongation of QTc-F >500 msec

- Clinically significant new or worsening signs of cervicomedullary compression as determined by the Investigator and in consultation with Sponsor medical monitor and neurosurgical specialist (if needed)
- Adverse findings on clinical hip exam or hip imaging assessments that are determined to be clinically significant as determined by the Investigator and in consultation with Sponsor Medical Monitor and orthopedic specialist (if needed)

If the subject meets any stopping criterion, after Investigator consultation with the BioMarin Medical Monitor and DMC, the subject may be re-challenged at the same dose. If the subject meets stopping criteria on re-challenge or if re-challenge at same dose is not clinically indicated, other options that may be considered include:

- Re-challenge at lower dose with consideration given to upward titration to tolerated dose
- Permanent treatment discontinuation (with an option of ongoing assessment in the study)

Cohort Stopping Criteria

For each cohort, a DMC review will be conducted if any of the following cohort stopping criteria occur in subjects treated with BMN 111. Temporary dosing suspension, permanent discontinuation of dosing, or dose reduction for the cohort(s) will be considered and the impact on all other age cohorts will be assessed.

- Any treatment-emergent AE assessed as at least Grade 4 by the Investigator and/or Sponsor Medical Monitor

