9.4.4 Directions for Administration

Refer to the Study Drug Injection Guide for complete BMN 111 or placebo preparation instructions.

The injection will be administered as a daily dose of BMN 111 15 µg/kg or placebo given as a single subcutaneous injection. The dose should be given at approximately the same time every day whenever possible. Following administration of each dose at clinic visits, subjects should be observed for 8 hours after the injection on Days 1 and 2; 4 hours on Days 3 and 8; and 1 hour on subsequent dosing visits. Subjects should be observed for 30 minutes after every injection that is not administered at the clinic. Subjects should have adequate food

intake prior to dosing. All subjects should have been well hydrated and fed in the hour prior to administration of BMN 111 or placebo.

Caregivers will administer BMN 111 or placebo at home once approved by the investigator and adequate training is demonstrated. Instructions on how to complete and document the training can be found in the Study Reference Manual.

A caregiver will be eligible to administer BMN 111 or placebo if he or she meets all of the following criteria:

- The subject has been on a stable dosing regimen for a minimum of 3 days
- PI has approved administration of BMN 111 or placebo by the caregiver
- The caregiver has completed the Administration Training conducted by qualified study site personnel and has been observed by the study site personnel to be able to adequately prepare the proper dose and perform the injections safely

For dosing between planned clinic visits prior to caregiver approval, a home health nurse may administer BMN 111 or placebo, or subjects may be administered BMN 111 or placebo in the clinic by study staff or trained caregiver.

The caregiver will be provided with a study diary and will be asked to record daily dosing information, changes in health status, medications and injection sites used, date and time of the injection, and injection site reactions, if any.

A subject's suitability for continued at-home drug administration will be evaluated by the investigator and the Sponsor's Medical Monitor if a subject experiences a CTCAE Grade 3 or higher AE that is considered possibly or probably drug-related, and/or a hypersensitivity reaction during the study.

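### With item z applied, Table 10.2.3.3.1 calls an AE related only when the drug is the sole or likelier cause, which is stricter than Section 10.1.1 and leaves some events in neither class

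*Protocol*

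**What the plan says.** The supplied text holds the protocol before this amendment in full, and the amended protocol only as far as Section 9.5.1. Section 10 is therefore visible only in its pre-amendment form, together with what the summary of changes says about it.

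- **First arm of *Related* (Table 10.2.3.3.1).** Before the amendment it required reasonable timing and that "The AE could possibly be explained by factors or causes other than exposure to the IP". Item z states "Error in Table 10.2.3.3.1 has been corrected to read" the opposite: the AE could not be so explained.
- **Second arm of *Related*.** Reasonable timing, and "The AE is more likely explained by exposure to the IP than by other factors or causes". The summary of changes lists no change here.
- ***Not Related* on etiology grounds.** Another cause is considered likely, which the table glosses as meaning that "there are no facts, evidence, or arguments to suggest a causal relationship to the IP". No change is listed.
- **Section 10.1.1.** "An adverse drug reaction is any AE for which there is a reasonable possibility that the study-drug caused the AE". Reasonable possibility, it adds, "means there is evidence to suggest a causal relationship between the study-drug and the AE". No change is listed.
- **Section 9.1.2 (amended).** One individual stopping criterion is "Any treatment-emergent AE of at least Grade 3 assessed as related to study drug by the Investigator and/or Sponsor Medical Monitor". The matching cohort criterion is the same event in any two subjects.
- **Section 9.4.4 (amended).** Suitability for home dosing is re-evaluated after a Grade 3 or higher AE "considered possibly or probably drug-related", or after a hypersensitivity reaction.
- **Synopsis, Safety Analysis (amended).** AE incidence is summarized by, among other things, relationship as assessed by the investigator.

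**The concern.** The table that investigators are told to use and the definition that it should implement set different thresholds. Section 10.1.1 sets a low bar: some evidence that the drug contributed. The table as amended sets a high one: the drug must be at least the likelier explanation. Events between the two bars have no assigned class, so the answer depends on how each investigator resolves the gap. Section 9.4.4 adds a graded scale that a two-class table cannot produce.

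This matters because safety is a primary objective and relatedness feeds a stopping criterion with a low count (two subjects) in small cohorts. The middle case is also likely to arise in this population. The protocol itself says that sleep-disordered breathing may affect up to 85% of children with achondroplasia. It lists feeding problems, apnea and cyanotic episodes among the disease's complications, and it gives pallor, lethargy and poor feeding as signs of drug-related hypotension. Drug and disease will often be competing explanations for the same event.

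**Working it through.** The plan gives no figure to reproduce. The main check is to set the passages side by side, for an AE reasonably related in time to dosing, with the table as amended by item z and otherwise unchanged.

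| Situation | Table before amendment | Table with item z | Section 10.1.1 |
|---|---|---|---|
| No evidence for the drug; another cause likely | *Related* (first arm) and also *Not Related* | *Not Related* | Not a reaction |
| Evidence for the drug; no other cause possible; drug likelier | *Related* (second arm) | *Related* | Reaction |
| Evidence for the drug; another cause possible; drug likelier | *Related* | *Related* | Reaction |
| Evidence for the drug; another cause possible; drug not likelier | *Related* (first arm) | **Neither class** | **Reaction** |

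Step by step:

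1. If nothing but the drug can explain the AE, the drug is already the likelier cause. The amended first arm is contained in the second, so *Related* reduces to the drug being more likely than the alternatives.
2. In the last row the drug is not the likelier cause, so neither arm of *Related* is met.
3. *Not Related* on etiology grounds is glossed as an absence of any evidence for the drug. In the last row there is evidence, so it is not met either. If the alternative is the likelier cause, the opening words of that arm are met while its gloss is not, so the arm disagrees with itself.
4. Section 10.1.1 calls the last row a reaction. This is the only row where the amended table and 10.1.1 disagree.
5. The pre-amendment table was also faulty. The first row qualified for both classes, so a correction was needed and undoing item z would not solve the problem.

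**Sensitivity of the two-subject cohort criterion (illustration only).** Inputs from the protocol: Cohort 1 has 3 sentinels plus at least 27 randomized 1:1, so 3 + about 13 = 16 children on BMN 111. Cohorts 2 and 3 each have 3 + at least 17 randomized 1:1, so 3 + about 8 = 11. Assumed, because the documents do not give them: the share p of treated children with a Grade 3 or higher AE that is a reasonable-possibility reaction, and the fraction c of these that is called related. With q = p × c and children independent, P(at least 2) = 1 − (1 − q)^n − n·q·(1 − q)^(n − 1).

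Example, n = 16, p = 0.10, c = 1: 1 − 0.9^16 − 16 × 0.1 × 0.9^15 = 1 − 0.185 − 0.329 = 0.485 (from unrounded terms).

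| n | p | c = 1 | c = 0.75 | c = 0.50 |
|---|---|---|---|---|
| 16 | 0.05 | 0.189 | 0.119 | 0.059 |
| 16 | 0.10 | 0.485 | 0.340 | 0.189 |
| 16 | 0.20 | 0.859 | 0.716 | 0.485 |
| 11 | 0.05 | 0.102 | 0.062 | 0.030 |
| 11 | 0.10 | 0.303 | 0.197 | 0.102 |
| 11 | 0.20 | 0.678 | 0.508 | 0.303 |

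The criterion is sensitive to how the middle row is resolved. The table says nothing about how often that row occurs or which way investigators would resolve it.

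**The case against.** The strongest reply has four parts.

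**The amended Section 10 is not shown.** The conflict is assembled from one line of the summary of changes and pre-amendment text. This is a real limit and must be stated. It does not remove the point: item z gives the new operative wording, and no change is listed to the second arm, to *Not Related* or to 10.1.1. The conflict is between the new wording and the protocol's own definition, not between a change log and superseded text.

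**Safeguards surround the table.** A reader might infer that expedited reporting is weakened. The documents do not support that for the site's duty: Section 10.4.1 sends all SAEs and events of special interest to the sponsor within 24 hours whatever the causality call. Section 10.2.3.3 has the sponsor evaluate every reported SAE regardless of the investigator's view. Only the sponsor's SUSAR classification (Section 10.4) could be touched, and that review stands in front of it. A reader might also infer that the stopping rules in general are affected. The Grade 4, hypotension, ECG and hip criteria, and the individual cervicomedullary compression criterion, do not use relatedness. For the criterion that does, the sponsor's medical monitor may also call an event related.

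**The direction is not fixed.** A reader might conclude that related events *are* undercounted. The gap leaves them unclassified. The table is headed as guidance and is followed by factors suggestive of causality, so an investigator could resolve the gap as *Related*. This objection stands: undercounting is possible, and so is inconsistency between sites.

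**The analysis effect is modest.** Safety analysis is descriptive, and AEs are also summarized by preferred term, seriousness and severity, by treatment group where applicable. The comparison of arms does not need investigator causality. This is fair, but the stopping criterion and the summaries by relationship do need it.

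**Conclusion.** The point holds as an internal conflict of definitions. With item z applied, *Related* means sole or more likely cause, while Section 10.1.1 requires only evidence to suggest a causal link. One type of event, with evidence for the drug and an equally or more plausible alternative, is a reaction under 10.1.1 and has no class in the table. Section 9.4.4 uses a scale that the table cannot supply.

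Its reach is limited to one individual and one cohort stopping criterion, the AE summaries by relationship and possibly SUSAR classification. The proportion of events affected cannot be derived from the documents; any percentage would rest on an assumed distribution of investigators' causal judgments, so none is offered. The conclusion assumes that the parts of Section 10 with no listed change are in fact unchanged. It should be corrected, because the stopping criterion depends on very few events and the repair is small.

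**What to change.** Check the amended Section 10 first. If it reads as assumed here:

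- Reconcile Table 10.2.3.3.1 with Section 10.1.1 so that the two classes are mutually exclusive and exhaustive. Every AE with a reasonable possibility of drug causation, as 10.1.1 defines it, goes to *Related*, including when another cause is also plausible. All others go to *Not Related*. State this explicitly for the case of an equally or more plausible alternative.
- Reconcile the relatedness wording in Section 9.4.4 with the table's two classes.
- Leave the stopping and home-dosing rules themselves as they are; only the causality definition feeding them needs to be consistent.

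The cost is a few lines of protocol text and matching eCRF guidance. Somewhat more AEs may be labelled related, which may make the related-AE table and the stopping criterion look slightly less favourable.
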